2. INTRODUCTION

2.1 Background and Study Rationale

An outbreak of COVID-19 caused by a novel SARS-CoV-2 began in Wuhan, Hubei Province, China in December 2019, and the disease has since spread globally (WHO 2020a). The World Health Organization (WHO) declared COVID-19 a pandemic on 11 Mar 2020; however, widespread community transmission was already occurring in many locations. As of 14 Jan 2021, more than 92 million cases and 1.9 million deaths worldwide have been attributed to the COVID-19 pandemic (JHU 2020; WHO 2020a).

ModernaTX, Inc has developed a vaccine platform based on the principle and observations that cells *in vivo* can take up mRNA, translate it, and then express protein viral antigen(s) on the cell surface. mRNA is highly precise in its translation into proteins that match viral antigens. The delivered mRNA does not enter the cell nucleus or interact with the genome, is nonreplicating, and is expressed transiently. The estimated half-life for mRNA after injection is approximately 8 to 10 hours, before degradation by native RNases in the body, but the duration of effect also depends on the half-life of the expressed protein, which persists in the body for several days. mRNA vaccines have been used to induce immune responses against infectious viral pathogens such as cytomegalovirus, human metapneumovirus, parainfluenza virus type 3, Zika, and influenza.

The mRNA-1273 encodes for the full-length spike (S) protein of SARS-CoV-2, modified to introduce 2 proline residues to stabilize the S protein (S-2P) in a prefusion conformation, derived from the Wuhan-Hu-1 strain (Corbett KS et al, 2020). The mRNA-1273 vaccine is currently being evaluated for safety and immunogenicity in a dose-ranging Phase 1 study sponsored by DMID (NCT04283461), for safety and immunogenicity in a Moderna-sponsored Phase 2a study (NCT04405076), and for safety, efficacy, and immunogenicity in a Moderna-sponsored Phase 3 study (NCT04470427). All three of these studies are ongoing and conducted in the US.

The primary efficacy objective of the Phase 3 study was met, with the vaccine efficacy of mRNA-1273 to prevent symptomatic COVID-19 disease observed to be 94.1%. The vaccine was also observed to be efficacious in preventing severe COVID-19. In December 2020 the FDA issued Emergency Use Authorization of mRNA-1273 (Moderna COVID-19 Vaccine) for active immunization to prevent COVID-19 in individuals 18 years of age and older.

Recently, SARS-CoV-2 variants with mutations in the S protein have emerged. A variant first identified in South Africa (B.1.351) is associated with increased transmission, higher viral burden, and possibly increased mortality in infected persons (Tegally H et al, 2020). To date, four vaccines, all based on the Wuhan-sequence of the S protein, have shown reduced activity against the B.1.351 variant. Sera from individuals vaccinated with mRNA-based vaccines had a 6-to-9-fold reduction in neutralizing activity against a B.1.351-matched pseudovirion relative to a Wuhan-matched pseudovirion (Wang P et al, 2021; Wu K et al, 2021). More recently, pivotal studies testing both viral vector and adjuvanted protein technologies had lower efficacy in regions where B.1.351 was known to be circulating (Callaway E & Mallapaty S; Cohen J, 2021). Hence, the development and testing of vaccines targeting this SARS-CoV-2 variant is urgently needed.

mRNA-1273.351, like mRNA-1273, encodes the prefusion stabilized S protein of SARS-CoV-2. However, the mRNA of mRNA-1273.351 incorporates the key mutations present in the B.1.351 strain of the virus. This phase 1 clinical trial will evaluate the immunological benefit of boosting subjects previously vaccinated with mRNA-1273 (DMID 20-0003) with the B.1.351 strain-specific S protein, as well as the breadth of response induced by vaccinating with mRNA-1273 and mRNA-1273.351 in naïve persons, who have not previously received a SARS-CoV-2 vaccine and are not known to have been previously infected with SARS-CoV-2.

Results from this study will inform the design of subsequent clinical studies of mRNA-1273.351. Plans for further clinical development are being drafted in consultation with regulatory authorities by Moderna. This will include evaluation in a subsequent Phase 2/3 study that will assess the safety and immunogenicity of both monovalent mRNA-1273.351 and multivalent mRNA-1273/mRNA-1273.351. These studies will assess both single-dose boosting at different dose intervals than the current study and a two-dose primary series at different dose levels in larger numbers of study participants.

2.1.1 Public Readiness and Emergency Preparedness Act

The study vaccines, mRNA-1273 and mRNA-1273.351, and the efforts for this clinical trial are covered under the Public Readiness and Emergency Preparedness Act (PREP Act) and the Declaration issued by the Secretary of the U.S. Department of Health and Human Services under that Act. Under the PREP Act and the Declaration, covered persons (such as manufacturers, distributors, program planners, and other qualified persons who prescribe, administer or dispense study product) are immune from liability from the administration, or use of a covered countermeasure, such as mRNA-1273 and mRNA-1273.351. The PREP Act provides immunity for covered persons from liability, unless the injury was caused by willful misconduct. The Declaration invoking the PREP Act for COVID-19 covered countermeasures was made on March 10, 2020 and is retroactively effective from February 4, 2020.

The PREP Act also established the Countermeasures Injury Compensation Program (CICP) to provide compensation for serious injuries or death that occur as the direct result of the administration or use of certain countermeasures. Any requests for compensation must be filed within one year of the administration or use of the covered countermeasure. Requests for Benefits must be made to the Health Resources and Services Administration's (HRSA) Countermeasures Injury Compensation Program (<http://www.hrsa.gov/cicp/>) by filing a Request for Benefits Form and all required medical records and supporting documentation. Additional information on filing a Request for Benefits is available on the CICP's website at <http://www.hrsa.gov/cicp/>. Compensation may then be available for reasonable and necessary medical benefits, lost wages and/or death benefits to eligible individuals for certain injuries in accordance with regulations published by the Secretary of HHS (found at 42 CFR part 110).

If an individual suffers a serious physical injury or death from the administration or use of a covered countermeasure in this study, the individual, the individual's legal or personal representative, the administrator/executor of a deceased individual's estate, or certain survivors may request benefits from the CICP. A serious physical injury means an injury that warranted hospitalization (whether or not the person was actually hospitalized) or that led to a significant loss of function or disability. The CICP is the payer of last resort. This means that it only covers expenses or provides benefits that other third-party payers (such as health insurance, the

Department of Veterans Affairs, or Workers' Compensation programs) do not have an obligation to pay.

If the Secretary of HHS does not make a final determination on the individual's request within 240 days, or if the individual decides not to accept the compensation, the injured individual or his representative may pursue a tort claim in the US District Court for the District of Columbia, but only if the claim involves willful misconduct and meets the other requirements for suit under the PREP Act. Any award is reduced by any public or private insurance or worker's compensation available to the injured individual. Awards for non-economic damages, such as pain, suffering, physical impairment, mental anguish, and loss of consortium are also limited. If the individual accepts compensation, or if there is no willful misconduct, then the individual does not have a tort claim that can be filed in a US Federal or a State court.

2.2 Risk/Benefit Assessment

2.2.1 Known Potential Risks

The potential risks of participating in this trial are those associated with having blood drawn, IM injection, possible reactions to the mRNA-1273 and mRNA-1273.351 vaccines, and breach of confidentiality.

Drawing blood may cause transient discomfort and fainting. Fainting is usually transient and managed by having the subject lie down and elevate his/her legs. Bruising at the blood draw site may occur but can be prevented or lessened by applying pressure to the blood draw site for a few minutes after the blood is taken. IM injection may also cause transient discomfort and fainting. Drawing blood and IM injection may cause infection. The use of aseptic (sterile) technique will make infection at the site where blood will be drawn or where the vaccination will be given extremely unlikely.

Risks of mRNA-1273 and mRNA-1273.351

Immediate systemic allergic reactions (e.g., anaphylaxis) can occur following any vaccination. These reactions are very rare and are estimated to occur once per 450,000 vaccinations for vaccines that do not contain allergens such as gelatin or egg protein (Zent O et al, 2002).

Anaphylactic reactions have occurred after administration of the Moderna and the Pfizer mRNA COVID-19 vaccines in vaccination campaigns under Emergency Use Authorization (EUA) in the United States. Most of these reactions had onset within 30 minutes of vaccination, most of these events occurred in persons with a prior history of allergy, and nearly all were women. The currently estimated risk of an anaphylactic reaction to the Moderna EUA COVID-19 vaccine is about 3 events per million vaccinations.

As a precaution, all subjects will remain under observation at the study site for at least 30 minutes after injection.

Infrequently, people who have received dermal fillers might experience swelling at or near the site of filler injection (usually face or lips) following administration of a dose of an mRNA COVID-19 vaccine. The swelling appears to be temporary and resolves with medical treatment, including corticosteroid therapy. COVID-19 vaccines can be administered to people who have received injectable dermal fillers who have no contraindications or precautions for vaccination.

Vasovagal syncope (fainting) can occur before or after any vaccination, is usually triggered by the pain or anxiety caused by the injection and is not related to the substance injected. Therefore, it is important that standard precautions and procedures be followed to avoid injury from fainting.

Intramuscular injection with other mRNA vaccines manufactured by ModernaTX, Inc containing the SM-102 lipid formulation commonly results in a transient and self-limiting local inflammatory reaction. This typically includes pain, erythema (redness), or swelling (hardness) at the injection site, which are mostly mild to moderate in severity and usually occur within 24 hours of injection. A small percentage of participants may experience late local inflammatory reactions, with onset seven or more days after, usually the first, vaccination, and characterized by redness in the deltoid area of the upper arm and/or pain or itching (Baden LR et al, 2020). These reactions are self-limited and are not a contraindication to subsequent vaccinations in the vaccination series.

The majority of local and systemic solicited adverse events (AEs) observed after injection with mRNA-1273 at the 100-mcg dose level have been mild to moderate in severity. The most commonly reported systemic AEs were headache, myalgia, fatigue, chills, and fever (Baden LR et al, 2020). In the majority of cases, the reactions resolved spontaneously within several days. Laboratory abnormalities (including increases in liver function tests and serum lipase levels) following injection were observed in clinical studies with similar mRNA-based vaccines. These abnormalities were without clinical symptoms or signs and returned toward baseline, pre-vaccination (Day 1) values over time. The clinical significance of these observations is unknown.

Recently, myocarditis and pericarditis have been reported rarely following vaccination with the Moderna COVID-19 EUA Vaccine. Although causality has not been established, the majority of cases have been in young males (<30 years old), occurring a few days to up to a week after the vaccination and seen more commonly after the second dose. However, cases have been reported in older males, females, as well as after the first dose of vaccine. Most cases are generally mild, and individuals tend to recover within a short time after treatment. However, long term outcomes are unknown. Additionally, it is not known whether the risks of myocarditis or pericarditis are increased following additional doses of vaccine.

Subjects will be informed of the potential risk of myocarditis or pericarditis and be advised to monitor for symptoms of myocarditis or pericarditis, including chest pain, shortness of breath, tachycardia, or palpitations. Subjects will be encouraged to immediately contact research staff and their medical provider if these symptoms occur following a study vaccination.

There is limited experience with administration of a third dose of the mRNA COVID-19 vaccines, and it is possible that the third dose may be associated with more frequent or more severe adverse events.

Further details are provided in the current IB for mRNA-1273. mRNA-1273.351 has not been tested clinically, but based on its similarity to mRNA-1273, the risks are expected to be similar.

Risks to Privacy

Subjects will be asked to provide personal health information (PHI). All attempts will be made to keep this PHI confidential within the limits of the law. However, there is a chance that unauthorized persons will see the subject's PHI. All study records will be kept in a locked file

cabinet or maintained in a locked room at the participating site. Electronic files will be password protected. Only people who are involved in the conduct, oversight, monitoring, or auditing of this trial will be allowed access to the PHI that is collected. Any publications from this trial will not use information that will identify subjects by name. Organizations that may inspect and/or copy research records maintained at the participating site for quality assurance (QA) and data analysis include groups such as the IRB, NIAID and the FDA.

A description of this clinical trial will be available on <http://www.ClinicalTrials.gov>, as required by US Law. This web site will not include information that can identify subjects.

There may be other risks, discomforts or side effects that are unknown at this time.

Risks of Genetic Testing

Any genetic data generated will be kept private. There may be a risk that information resulting from research genetic testing could be misused for discriminatory purposes. However, state and federal laws provide protections against genetic discrimination. Researchers will need to maintain confidentiality in order to be granted access to genetic information.

2.2.2 Known Potential Benefits

There is no direct benefit to the subjects. There is potential benefit to society resulting from insights gained from participation in this study due to the emerging threat of the SARS-CoV-2 outbreak. Data from the Phase 3 placebo-controlled clinical trial of mRNA-1273 demonstrated 94.1% efficacy of the vaccine when 100 mcg is administered as a two-vaccination series versus placebo against SARS-CoV-2 infection. The efficacy of other dosages of mRNA-1273 (e.g., 25, 50, or 250 mcg) is not known. The doses and vaccination strategies used in this trial may or may not alter this protection. It is unknown if the mRNA-1273.351 vaccine will provide protection against infection with the B.1.351 variant.

3. OBJECTIVES AND ENDPOINTS

Table 6: Objectives and Endpoints (Outcome Measures)

OBJECTIVES	ENDPOINTS (OUTCOME MEASURES)
Primary	

To evaluate the safety and reactogenicity of mRNA-1273 and mRNA-1273.351 vaccines, in naïve and previously vaccinated individuals.	
Frequency and grade of each solicited local and systemic reactogenicity AE during a 7-day follow-up period post each vaccination.Frequency and grade of any unsolicited AEs during the 28-day follow-up period post each vaccination.Frequency of any SAEs, Protocol Specified AESIs, NOCMCs, and MAAEs

OBJECTIVES	ENDPOINTS (OUTCOME MEASURES)
	from the first vaccination through 12 months after the last vaccination.
Secondary	

To assess humoral immunogenicity of mRNA-1273 and mRNA-1273.351 vaccines, in naïve and previously vaccinated individuals.	
Response rate, and magnitude of SARS-CoV-2-specific antibody binding and neutralization titers in serum samples as assessed via a range of assays at all timepoints.
Exploratory	

To assess, in at least a subset of samples the innate immune response and B cell response following vaccination.	
Magnitude, phenotype, and percentage of innate immune cells and SARS-CoV-2 specific B cells, as measured by flow cytometry, and targeted B cell repertoire analysis at different timepoints post vaccination relative to baseline.

To assess, in at least a subset of samples, the SARS-CoV-2 S protein-specific T cell responses.	
Magnitude, phenotype, and percentage of cytokine producing S protein-specific T cells, as measured by flow cytometry at different timepoints post vaccination relative to baseline.

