4. STUDY DESIGN

4.1 Overall Design

This is a phase 1, open-label, randomized clinical trial in males and non-pregnant females, 18 years of age and older, who are in good health, have no known history of COVID-19 or SARS-CoV-2 infection, and meet all other eligibility criteria. This clinical trial is designed to assess the safety, reactogenicity and immunogenicity of mRNA-1273.351 manufactured by ModernaTX, Inc, given in vaccination schedules alone, sequentially, or coadministered with mRNA-1273. mRNA-1273.351 is a novel LNP-encapsulated mRNA-based vaccine that encodes for a full-length, prefusion stabilized S protein of the SARS-CoV-2 B.1.351 variant. Enrollment will occur at approximately five domestic clinical research sites.

This study includes two cohorts. Cohort 1 will provide rapid information about the immunogenicity of mRNA-1273.351 in a previously vaccinated group. This cohort can inform near term public health decisions if the variant virus becomes more widespread. Cohort 2 will evaluate different strategies for generation of cross protective immune responses in a naïve population. This cohort will take longer to provide information on the immunogenicity of

mRNA-1273.351, but is important to inform future public health strategies. As Cohorts 1 and 2 are in different populations, they can be enrolled in parallel as determined by each site.

Cohort 1 will include subjects 18 years of age and older who received two vaccinations of mRNA-1273 at dosages of 50 mcg, 100 mcg, or 250 mcg in the Phase 1 clinical trial (DMID 20-0003). Those subjects will be offered enrollment into this study approximately 9 to 12 months after they received the second vaccination in DMID 20-0003. At enrollment in this study, their long-term follow-up in DMID 20-0003 will be terminated. Subjects will be randomized, within each of the DMID 20-0003 cohorts (age and dosage groups – 50 mcg, 100 mcg, and 250 mcg), 1:1 (as outlined in Table 7) to either:

- Arm 1A, vaccination with a 50-mcg dose of the mRNA-1273.351 variant, or
- Arm 1B, vaccination with a combination vaccination that includes 25 mcg of mRNA-1273 and 25 mcg of mRNA-1273.351.

The anticipated sample size to be drawn from the DMID 20-0003 study population is approximately 45 subjects 18 through 55 years of age and approximately 20 subjects 56 years of age and older.

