Subjects in Cohort 1 will receive a single intramuscular (IM) injection of the designated vaccine and will be followed through 12 months after vaccination. Follow-up visits will occur on Days 8, 15, and 29, as well as 3, 6, and 12 months after the vaccination.

Table 7. Cohort 1 Treatment Arms

Arm	Sample Size	Vaccination Product and Dose
1A	~30	50 mcg mRNA-1273.351
1B	~30	25 mcg mRNA-1273 + 25 mcg mRNA-1273.351

Cohort 2 will include approximately 150 participants 18 through 55 years of age who have not received a COVID-19 vaccine, have no known history of COVID-19 or SARS-CoV-2 infection, and do not have underlying conditions that are associated with an increased risk of severe illness from SARS-CoV-2 infection. Enrollment may close before the full 150 participants based on estimates on the timing of immunogenicity results and the need to inform public health decisions. They will be randomly assigned to one of 8 treatment arms and will receive 2 or 3 IM injections of the vaccine (as outlined in Table 8), and followed through 12 months after the last vaccination. Follow-up visits will occur 7, 14, and 28 days after each vaccination, as well as 3, 6, and 12 months post the last vaccination.

Table 8: Cohort 2 Treatment Arms

Arm	Sample Size	First Vaccination	Second Vaccination		Third Vaccination	
		Product and Dose	Interval	Product and Dose	Interval	Product and Dose
2A	15	100 mcg mRNA-1273	28 days	100 mcg mRNA-1273	28 days	50 mcg mRNA-1273.351
2B	15	50 mcg mRNA-1273	28 days	50 mcg mRNA-1273	28 days	50 mcg mRNA-1273.351
2C	20	100 mcg mRNA-1273.351	28 days	100 mcg mRNA-1273.351		None
2D	20	50 mcg mRNA-1273.351	28 days	50 mcg mRNA-1273.351		None
2E	20	100 mcg mRNA-1273	28 days	100 mcg mRNA-1273.351		None
2F	20	50 mcg mRNA-1273	28 days	50 mcg mRNA-1273.351		None
2G	20	50 mcg mRNA-1273 + 50 mcg mRNA-1273.351	28 days	50 mcg mRNA-1273 + 50 mcg mRNA-1273.351		None
2H	20	25 mcg mRNA-1273 + 25 mcg mRNA-1273.351	28 days	25 mcg mRNA-1273 + 25 mcg mRNA-1273.351		None

Summary of Treatment Arms:

- 2A: Evaluates the mRNA1273 EUA vaccination series, plus a variant vaccine as a third dose.
- 2B: Evaluates a 50-mcg vaccination series, plus a variant vaccine as a third dose.
- 2C-2D: Evaluate 2 doses of the homologous variant vaccine at different dose levels.
- 2E-2F: Evaluate heterologous prime-boost strategies at 2 dose levels.
- 2G-2H: Evaluate a 1:1 mix of vaccine (2 doses), with the total dose for both vaccines equal to 100 mcg and 50 mcg, respectively.

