9.4.3 Analysis of the Secondary Endpoint(s)

Summaries and analysis of immunogenicity data will be presented for the mITT population. If there are protocol deviations which may affect the analysis, a per-protocol (PP) analysis may also be performed.

Seroconversion is defined as a 4-fold increase in antibody titer over baseline.

Seroconversion rates, GMFR and GMT for SARS-CoV-2 as measured by a range of assays measuring total Spike-specific IgG (ELISA-based) and function (neutralization, receptor binding domain (RBD) binding, or similar) will be calculated for all timepoints by arm and will be summarized graphically. Seroconversion rates, GMFR and GMT will be presented with their corresponding 95% CI estimates at each timepoint and overall peak GMT.

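### First-dose immunogenicity is summarised by arm although Arms 2A and 2E, and Arms 2B and 2F, have by then received the same vaccine and dose; pooling each pair gives n=35 instead of 15 or 20

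*Protocol*

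**What the plan says.** **Immunogenicity.** Section 9.4.3 states that the titre summaries "will be calculated for all timepoints by arm and will be summarized graphically". Section 9.4.9 likewise summarises B-cell, innate and T-cell data at each timepoint by arm. Section 9.4.6.2 allows optional interim analyses by vaccine schedule group, a term it does not define.

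**Safety.** Section 9.4.4 plans proportions with exact confidence intervals but does not say whether they are by arm, by product or pooled.

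**Arms.** In Table 8, 2A (n=15) and 2E (n=20) both start with 100 mcg of mRNA-1273, and 2B (n=15) and 2F (n=20) both start with 50 mcg. The pairs part at the second dose: 2A and 2B receive mRNA-1273 again, while the design summary says "2E-2F: Evaluate heterologous prime-boost strategies at 2 dose levels". Section 6.3.2 randomises all eight arms together, 3:3:4:4:4:4:4:4, with no stratification in Cohort 2.

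**Objectives.** The primary objective in Table 6 is "To evaluate the safety and reactogenicity of mRNA-1273 and mRNA-1273.351 vaccines, in naïve and previously vaccinated individuals". The secondary one is "To assess humoral immunogenicity of mRNA-1273 and mRNA-1273.351 vaccines, in naïve and previously vaccinated individuals". Sections 4.1 and 9.1 put the aim more narrowly, as mRNA-1273.351 given by itself, in sequence with mRNA-1273, or together with it.

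**The concern.** Between the first dose and the second, the arm label in each pair refers only to a dose not yet given. Day 15 and Day 29 results in 2A and 2E are two random samples of the same treatment in the same population, and so are those in 2B and 2F. Reporting them only by arm gives two imprecise estimates of one quantity. It also invites readers to interpret differences between rows that can only be chance, apart from any effect of knowing the assignment.

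What is at stake is precision in a trial whose sole purpose is estimation. The first-dose response to mRNA-1273 is the natural yardstick for the first-dose responses in 2C and 2D (variant) and 2G and 2H (mixture). Sections 1.1 and 4.1 allow enrollment to close before 150, so the arms may be smaller than planned.

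**Working it through.** **Inputs.** Arm sizes are from Table 8 and the randomisation ratio from section 6.3.2: 150 × 3/30 = 15 and 150 × 4/30 = 20. Tables 10 and 11 show the same first-dose sampling in the three-dose and two-dose arms: 16 mL of serum for serology at Days 1, 15 and 29, and 64, 48 and 40 mL for PBMCs on those days. The second dose falls on Day 29.

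**Pooled size.** 2A+2E = 15 + 20 = 35; 2B+2F = 15 + 20 = 35.

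**The plan's own figures.** Table 12 uses 1 − (1 − p)^n. At p = 20% this gives 96.5% for n=15 and 98.8% for n=20, as printed. All the printed entries for n = 15, 20, 30 and 60 reproduce. For Cohort 2, section 9.2 considers n = 15, 20 and 150, never 35.

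**GMT.** The 95% interval on the log scale has half-width t(0.975, n−1) × s/√n:

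- n=15: 2.145 s/3.873 = 0.554 s
- n=20: 2.093 s/4.472 = 0.468 s
- n=35: 2.032 s/5.916 = 0.344 s

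The ratios are 0.344/0.554 = 0.62 and 0.344/0.468 = 0.73. The interval is therefore about 38% narrower than with n=15 and 27% narrower than with n=20. The protocol gives no SD, but s cancels, so the ratios hold for any common SD. The same ratios apply to GMFR.

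**Response rate near 50%** (exact Clopper-Pearson 95% interval):

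- 7/15: 21.3% to 73.4%, width 52 points
- 10/20: 27.2% to 72.8%, width 46 points
- 17/35: 31.4% to 66.0%, width 35 points

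**Safety, if grouped the same way.**

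| n | Chance of at least one event at a true 5% rate, 1 − 0.95^n | Upper limit of two-sided exact 95% interval after zero events, 1 − 0.025^(1/n) |
|---|---|---|
| 15 | 53.7% | 21.8% |
| 20 | 64.2% | 16.8% |
| 35 | 83.4% | 10.0% |

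**Objectives against arms.** In Cohort 1 the choices are "Arm 1A, vaccination with a 50-mcg dose of the mRNA-1273.351 variant" and "Arm 1B, vaccination with a combination vaccination that includes 25 mcg of mRNA-1273 and 25 mcg of mRNA-1273.351", so 0 of about 60 previously vaccinated subjects receive mRNA-1273 alone. In Cohort 2, mRNA-1273 alone is given to 15 + 15 + 20 + 20 = 70 subjects at dose 1 and to 15 + 15 = 30 at dose 2. The variant follows at Day 29 in 2E/2F and at Day 57 in 2A/2B.

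**The case against.** **Pooling can be left to the SAP.** The protocol promises a full SAP and abbreviated analysis plans, and a commitment to by-arm summaries does not forbid an extra pooled row. For safety this objection stands in full: section 9.4.4 names no unit. A reader might infer from the by-arm wording elsewhere that the primary safety endpoint is also reported separately for identical groups, but nothing in the document says so. For immunogenicity and cellular data it stands only in part. The unit there is fixed as the arm at every timepoint, so an SAP that follows the protocol need not produce the pooled summary.

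**The trial is open-label.** Knowing the later schedule could shift symptom reporting between pooled arms. This bears on solicited events and hardly on titres, and arm-wise rows beside the pooled row would show it.

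**A reader might infer that half of the objective cannot be answered.** The documents do not support that. Table 6 never says mRNA-1273 must be given alone. Three of the four product-by-population combinations have recipients of the product alone: mRNA-1273 in naive subjects (2A, 2B, 2E, 2F), the variant in naive subjects (2C, 2D) and the variant in previously vaccinated subjects (1A). The fourth is present as a component in 1B. For mRNA-1273 in naive subjects the 7-day and 28-day endpoints have complete windows. Only the long-term endpoint, "from the first vaccination through 12 months after the last vaccination", runs into the variant dose, and it describes a regimen rather than a product.

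**A reader might also infer that the plan claims a strain advantage it cannot show.** Section 2.1 does say the trial will "evaluate the immunological benefit of boosting subjects previously vaccinated with mRNA-1273 (DMID 20-0003) with the B.1.351 strain-specific S protein", and there is no mRNA-1273 booster arm. But no superiority over such a booster is claimed, section 9.1 disclaims any hypothesis test, and section 9.4.3 already analyses change from baseline.

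**Conclusion.** The point holds for the immunogenicity summaries in 9.4.3 and 9.4.9. Up to Day 29 they divide two groups of 35 identically treated subjects into 15 and 20. Pooling narrows the GMT interval by about 38% or 27% and the response-rate interval near 50% by about 17 or 11 points (52 or 46 down to 35). This is a clear improvement at almost no cost; it does not correct an invalid analysis, and no stated sample-size figure is wrong.

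The conclusion assumes full enrollment, valid samples from every subject, a common SD across pooled arms, and that blood on Day 29 is drawn before the second dose, which the schedule does not state explicitly. If enrollment closes early but the allocation ratio holds, each pooled group is still 7/30 of the cohort against 3/30 or 4/30, so the relative gain is similar.

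For safety, the same grouping is a suggestion. The breadth of Table 6 relative to 4.1 and 9.1 is a minor wording matter.

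**What to change.** 1. In 9.4.3 and 9.4.9, add a summary of Day 15 and Day 29 (pre-dose) results by first-dose product and dose: 2A+2E (100 mcg mRNA-1273, n=35) and 2B+2F (50 mcg mRNA-1273, n=35) beside 2C, 2D, 2G and 2H. Keep arm-wise reporting from the second dose onward; arm-wise rows for the first-dose period can stay next to the pooled ones.
2. In 9.4.4, state the grouping unit. The same pooled grouping is suggested for solicited events after dose 1 and unsolicited events to Day 29.
3. Optionally, align Table 6 with 4.1 and 9.1. Note that Cohort 1 data describe boosts containing mRNA-1273.351, and that mRNA-1273 alone is observed in naive subjects only to Day 29 (2E/2F) or Day 57 (2A/2B).

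The cost is one extra table and a few sentences, with no new subjects, arms, visits or samples. The downside is the possible small expectation difference between pooled open-label arms.
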